### Pre-Infusion:

- Eligibility Review
- Review of medical and cardiac history, and concomitant medications
- Cardiac physical examination
- Measurement of vital signs (temperature, HR, BP, and RR)
- 12-Lead ECG
- Venous blood will be collected for the following:
  - Clinical laboratory tests: chemistry, hematology
  - Coagulation if subject is taking warfarin
- Serial venous collection for cardiac enzymes (Troponin and CK-MB)
- A urine sample will be collected for urinalysis
- Adverse event assessment

### Infusion

Reference Section 6.10 for complete infusion details

### Post-infusion (D0-D1):

- Serial collection of vital signs (temperature, HR, BP, and RR) every 8 hours ( $\pm$  30 minutes) from the end of the infusion.
- Cardiac Physical Examination
- 12-lead ECG
- Serial venous collection for cardiac enzymes (Troponin and CK-MB)
- Venous blood will be collected for clinical laboratory tests: chemistry, hematology, and urinalysis

Following intracoronary infusion, subjects will be observed in the hospital for 20-24 hours with continuous cardiac (telemetry) monitoring. Troponin and CK-MB laboratory studies will be monitored every 8 hours ( $\pm$ 30 minutes) from the end of the infusion. A total of three

sets of cardiac enzymes will be evaluated to rule out cardiac injury during the post-infusion hospital stay through discharge. If the subject is discharged prior to 24 hours, cardiac enzymes will be drawn just prior to discharge.

*Day 1 Prior to Hospital Discharge:*

- Review of concomitant medications
- Adverse event assessment
- Physical assessment (chest pain, infusion/arterial puncture site(s))
- Review of lab results and 12-lead ECG

Prior to discharge from the hospital, a physical assessment will be performed which will include chest pain assessment, review of laboratory results, 12-lead ECG, and arterial puncture site as well as assessment of adverse events. In the absence of serious adverse events, subjects will be discharged per standard of care practice.

**Day 1 for ALL SUBJECTS:**

- Initiate 72-hour continuous cardiac rhythm monitoring using sponsor-supplied monitor system (indicated for home use)
- No study visit is required for Day 1, as subjects will receive prior instruction on use of the monitoring system

### **7.3 Day 3 Phone Visit**

The investigator's site staff will contact the subject (or parent/guardian) by telephone on Study Day 3 (3 days post Day 0) for safety follow-up. Study Day 3 is 3 days post-infusion for subjects randomized to CAP-1002. For subjects randomized to usual care, Study Day 3 is ten days after randomization.

The site will inquire as to the subject's overall health and whether the subject has had any adverse events, especially any requiring hospitalization or other medical intervention, in the preceding 2 days (i.e., Day 1 – Day 3).

If necessary, the phone call may be conducted on Study Days 4, 5, or 6.

If the site is unable to reach the subject by telephone, the site should make two more attempts to contact the subject, one each on the next two days.

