#### 7.13.2 Timing

Adverse event assessment and documentation will occur at every study visit from screening throughout the study. On the day of treatment administration, a subject's medical complaint will be considered to be a treatment-emergent adverse event if the event occurs any time after the first exposure of investigational product at the beginning of the catheterization for the infusion of CAP-1002. For subjects receiving usual care, an event is considered treatment-emergent if it occurs on or after 9:00 am (in the subject's time zone) on Day 0.

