## Appendix 1 Schedule of Events

Procedure / Event	Screening	Infusion (CAP-1002 only) 		Day 1 (Home)	Day 3 (Phone)	Week 2	Week 6	Month 3	Month 6	Month 12	Early Termination 
Study Day	≤30 days prior to randomization	Day 0		Day 1 	Day 3 (+3)	Day 14 (±3)	Day 40 (±7)	Day 90 (±7)	Day 180 (±14)	Day 360 (±30)	As Needed
		PRE	POST								
Informed Consent	X										
Eligibility Assessment	X	X									
Demographics	X										
Medical History	X	X									
Cardiac History	X	X									
Concomitant Medications	X	X	X			X	X	X	X	X	X
Vital Signs	X	X	X			X	X	X	X	X	X
Weight	X								X	X	X
Height 	X						X	X	X	X	X
12-Lead ECG	X	X	X			X	X	X	X	X	X
Limited Physical Examination	X									X	X
Cardiac Physical Examination	X	X	X			X	X	X	X	X	X
Cardiac MRI	X								X	X	X
Continuous cardiac rhythm monitoring	X			X			X		X	X	X
Clinical Laboratory Tests (includes Chemistry, Hematology, Urinalysis)	X	X	X			X	X	X	X	X	X
Serology 	X										
Osteopontin	X					X	X	X	X	X	X
ST2	X					X	X	X	X	X	X
IL-10	X					X	X	X	X	X	X
Galectin-3	X					X	X	X	X	X	X
Exploratory Biomarkers	X					X	X	X	X	X	X

Procedure / Event	Screening	Infusion (CAP-1002 only) 		Day 1 (Home)	Day 3 (Phone)	Week 2	Week 6	Month 3	Month 6	Month 12	Early Termination 
Study Day	≤30 days prior to randomization	Day 0		Day 1 	Day 3 (+3)	Day 14 (±3)	Day 40 (±7)	Day 90 (±7)	Day 180 (±14)	Day 360 (±30)	As Needed
		PRE	POST								
HLA	X										
DSA	X					X	X	X	X	X	X
ELISpot	X						X				
PUL scale	X						X	X	X	X	X
6MWT	X						X	X	X	X	X
Pediatric QL Inventory	X						X	X	X	X	X
PODCI	X						X	X	X	X	X
Spirometry	X						X	X	X	X	X
Coagulation		X									
Serum Troponin & CK-MB	X	X	X			X			X	X	X
Intracoronary Infusion			X								
Adverse Event Assessment	X	X	X		X	X	X	X	X	X	X

 Day 0 is the infusion date for subjects randomized to CAP-1002. All items listed for Infusion visit and assessments on Day 0 are only applicable for subjects randomized to CAP-1002. Subjects randomized to Usual Care do not have a Day 0 visit.

 Early Termination Visit procedures to be completed at time of withdrawal, should subject be withdrawn before Month 12 Visit. A Cardiac MRI will be conducted provided the subject's most recent study-related Cardiac MRI was conducted at least three months (i.e., 12 weeks) prior to the Early Termination Visit.

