 For eligible subjects randomized to the usual care arm, Day 1 is established as 8 days after the date of randomization, without an actual Day 1 visit. All study subjects initiate 72-hour continuous cardiac rhythm monitoring on Day 1.

 If standing height cannot be measured, height will be calculated using a measurement of ulna length (Gauld et al 2004).

 Serology includes HIV and hepatitis testing

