## 12. CLINICAL EVENTS COMMITTEE

In order to apply some level of consistency and standardization, the following will be adjudicated by a CEC:

- Clinical event endpoints
- AEs occurring within 24 hours of IP administration or reference time point (peri-procedural AEs)
- AEs judged by the investigator as possibly, probably or definitely related to the IP or IP administration procedure (related AEs)
- Treatment-emergent SAEs

The CEC will follow consensus definitions of cardiovascular endpoint events. In the case where the protocol explicitly provides an endpoint definition, the CEC will adjudicate the clinical event according to the protocol definition and then, separately, according to the consensus definition. In the case where the protocol provides only a partial definition (e.g., “emergency room treatment for heart failure”) or is silent on the definition of the endpoint, the consensus definition, if it exists, will be used.

For safety endpoints, a hierarchy will be applied for a clinical event that could be adjudicated in multiple categories so that a clinical event is counted only once. The hierarchy, from highest severity to lowest, will be death > heart failure hospitalization > cardiovascular-related hospitalization.

For any AE submitted to the CEC, all of the above characteristics will be adjudicated. In addition, the CEC can combine AEs reported separately into a single AE, can change the event description (i.e., the term used to report the AE), and can change the status of the reported event to a non-AE.

Any adjudicated event not otherwise named in the consensus definitions, as well as changed event descriptions, will be MedDRA-coded.

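### The Day 3 call's adverse-event question starts at Day 1, so usual-care events on Day 0 are not asked about directly until Week 2

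*Protocol*

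**What the plan says.** **The call.** Protocol 7.3 applies to both arms. Staff ask how the subject is in general and about "adverse events, especially any requiring hospitalization or other medical intervention, in the preceding 2 days", with Day 1 to Day 3 given in brackets as the meaning. On timing it says "For subjects randomized to usual care, Study Day 3 is ten days after randomization", and it adds "If necessary, the phone call may be conducted on Study Days 4, 5, or 6".

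**The usual-care clock.** Under Protocol 7.13.2, for usual care, "an event is considered treatment-emergent if it occurs on or after 9:00 am (in the subject's time zone) on Day 0". Protocol 3.3 and 9.5.2 and SAP 2.3.1 use the same reference time.

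**Usual-care contacts.** Protocol Appendix 1, footnote 1: "Subjects randomized to Usual Care do not have a Day 0 visit". Footnote 3 says of that arm that "Day 1 is established as 8 days after the date of randomization, without an actual Day 1 visit"; subjects start the home rhythm monitor that day. After the call, the next scheduled adverse-event assessment is Week 2, Day 14 ± 3 (Protocol 7.4).

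**CAP-1002 contacts.** Protocol 7.2 gives these subjects 20-24 h of in-hospital telemetry, serial enzymes, laboratory tests, and an adverse-event assessment both before infusion and before discharge.

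**Use of the data.**
- SAP 9.1 compares the arms on peri-procedural events other than TIMI/TMPG, with a 90% CI for the difference and a one-sided exact p-value. By SAP 2.3.1 these are sudden death and MACE within 72 h.
- SAP 12 sends to the events committee "AEs occurring within 24 hours of IP administration or reference time point (peri-procedural AEs", which covers both arms.
- SAP 9.2 plans a separate 24 h table, described by IP administration alone, with a between-arm p-value only where applicable.

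**The concern.** A look-back that begins on Day 1 suits the infused arm, whose Day 0 is already covered by the hospital stay. It does not suit usual care, where the call is the first scheduled contact after the clock starts and its adverse-event question leaves out the first hours of that clock. Solicitation is therefore uneven at the point where the plan sets up a usual-care reference for the infusion period. Safety is the primary objective, and with about 12 subjects per arm one subject with an unrecorded event moves an arm's incidence by 1/12 = 8.3 percentage points.

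**Working it through.** **The plan's own dates.** Usual-care Day 0 is randomization + 7 days, so Day 3 is 7 + 3 = 10 days after randomization, as stated. Two days before Day 3 is Day 1, as stated. Both reproduce.

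**Unasked time, calendar-day reading (call on Day 3).** The usual-care window opens at 9:00 am on Day 0 and the question reaches back to the start of Day 1. From 9:00 am to midnight is 15 h.
- Share of the 24 h window: 15/24 = 62.5%.
- Share of the 72 h window: 15/72 = 20.8%.

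**Literal 48 h reading.** A Day 3 call at 9:00 am reaches back 24 h short of the reference time; one at 5:00 pm reaches back 32 h short.
- 24 h window: all of it is unasked.
- 72 h window: 24/72 = 33% to 32/72 = 44% is unasked.

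**Late calls.** The 72 h window closes at 9:00 am on Day 3. If two days is counted back from the actual call day, as the protocol counts from Day 3:

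| Call day | Look-back starts | Hours after reference | Share of 72 h window unasked |
|---|---|---|---|
| 4 | Day 2 | 15 + 24 = 39 | 39/72 = 54% |
| 5 | Day 3 | 39 + 24 = 63 | 63/72 = 88% |
| 6 | Day 4 | 63 + 24 = 87 | 100% |

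If the bracketed Day 1 to Day 3 is fixed instead, the figure stays at 20.8%. The text does not say which applies.

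**First unrestricted assessment.** Week 2 is Day 14 − 3 = 11 to 14 + 3 = 17, so a Day 0 event is recalled over 11 to 17 days.

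**Illustration of consequence (24 h window).** Assumptions, none from the documents except the arm size: the same true incidence p in both arms, timing uniform over the window, 12 per arm, full recording in CAP-1002, and a fraction s of usual-care Day 0 events recovered at Week 2. Observed usual-care incidence = p × [1 − 0.625 × (1 − s)]. The last column is the chance of one-sided Fisher p ≤ 0.05 against CAP-1002 when there is no true difference, by exact enumeration.

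| p | s | Observed usual care | False positive |
|---|---|---|---|
| 25% | 100% | 25.0% | 2.2% |
| 25% | 50% | 17.2% | 5.6% |
| 25% | 0% | 9.4% | 13.2% |

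With s running from 100% to 0%, the range is 0.8% to 1.6% at p = 10% and 3.2% to 38.3% at p = 50%. For the 72 h window at p = 25% it is 2.2% to 4.1%. The default test in SAP 7.3 is two-sided; a two-sided Fisher p-value is never below the one-sided one, so for the 24 h table these are upper limits in this direction.

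**The case against.** The case for leaving the plan alone has force.

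- **Nothing is lost by rule.** A reader might infer that usual-care Day 0 events drop out. The documents do not support that: the call also asks about general health, so an event can be volunteered, and the Week 2 assessment has no stated look-back limit. This stands; the defect is late, uneven solicitation.
- **The 72 h comparison is little exposed.** A reader might infer that 20.8% of it is compromised. Its events are death, non-fatal MI and cardiovascular hospitalization, which are unlikely to be forgotten because a telephone question omitted 15 h. This stands.
- **The 24 h comparison is not firmly planned.** A reader might take 24 h events as simply compared between arms. SAP 12 commits only to adjudicating them in both arms. The SAP 9.2 table is worded around IP administration and its p-value is conditional. This stands.
- **The late-call figures rest on one reading.** The bracketed days may fix the window whatever the call date. That is fair, and it leaves an ambiguity to remove rather than a proven loss.
- **The percentages are clock time.** The documents give no background event rate and no recovery rate, so the illustration shows what its assumptions imply, not what will happen in this trial.
- **The script is the smaller asymmetry.** Telemetry, enzymes and laboratory tests in one arm, with an open control and no sham procedure (Protocol 3.4), produce a detection difference that no rewording removes.

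What survives all of this is that the adverse-event question, as written, omits a stretch of the usual-care clock that could be covered at no cost.

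**Conclusion.** The point holds as a minor gap in data collection. For usual care, 15 h of clock time after the reference point (62.5% of the 24 h window, 20.8% of the 72 h window, on the calendar-day reading of a Day 3 call) gets no direct adverse-event question until Day 11 to 17. The practical exposure is minor adverse events in the 24 h window. The likely direction is under-counting in usual care, so CAP-1002 would look worse; that error does not hide harm, but it blurs how much of an early excess is due to treatment. Any effect on a p-value depends on assumed incidence and recovery. The documents do not support calling the safety comparison invalid, or claiming that a corrected call would make ascertainment equal.

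**What to change.** Reword the question in Protocol 7.3 and the call script to: *any adverse events since Day 0 (from 9:00 am for usual care, from the start of the infusion procedure for CAP-1002) up to the time of this call*. Keep that look-back for calls on Days 4 to 6, which removes the ambiguity. The unasked Day 0 period then falls from 15 h to 0 h. A call at or after 9:00 am on Day 3, or on Days 4 to 6, can cover the whole usual-care 72 h window.

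State in the report that detection over the first day still differs between arms because of the in-hospital telemetry, enzymes and laboratory tests in the CAP-1002 arm.

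Cost: one line of script and one sentence in the report, with no added visit or contact. The change fits the purpose given for the call in the Amendment 2 log (Protocol Appendix 5), cited here for intent only: to assess adverse events in both arms between Day 0 and Week 2.

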### **7.4 Week 2 Visit (Day 14 ± 3 days)**

Subjects will return to the clinical site and complete the following procedures:

- Adverse event assessment
- Review of concomitant medications
- Measurement of vital signs (temperature, HR, BP, and RR)

- 12-Lead ECG
- Cardiac Physical Examination
- Venous blood will be collected for the following:
  - Clinical laboratory tests: serum chemistry, hematology
  - Cardiac enzymes: Troponin and CK-MB
  - Biomarkers: Osteopontin, ST2, IL-10, and Galectin-3
  - Exploratory biomarkers (if consent/assent provided)
  - Immunoassay: DSA
- A urine sample will be collected for urinalysis

### 7.5 Week 6 Visit (Day 40 ± 7 days)

Subjects will return to the clinical site and complete the following procedures:

- Adverse event assessment
- Review of concomitant medications
- Measurement of vital signs (temperature, HR, BP, and RR) and height
- 12-Lead ECG
- Cardiac Physical Examination
- 72-hour continuous cardiac rhythm monitoring using sponsor-supplied device
- Venous blood will be collected for the following:
  - Clinical laboratory tests: serum chemistry, hematology
  - Biomarkers: Osteopontin, ST2, IL-10, and Galectin-3
  - Exploratory biomarkers (if consent/assent provided)
  - Immunoassay: DSA and ELISpot
- A urine sample will be collected for urinalysis
- PUL Scale
- 6MWT (if capable)
- Pediatric QL Inventory
- PODCI
- Spirometry

### 7.6 Month 3 Visit (Day 90 ± 7 days)

- Subjects will return to the clinical site and complete the following procedures:
- Adverse event assessment
- Review of concomitant medications
- Measurement of vital signs (temperature, HR, BP, and RR) and height
- 12-Lead ECG
- Cardiac Physical Examination

- Venous blood will be collected for the following:
  - Clinical laboratory tests: serum chemistry, hematology
  - Biomarkers: Osteopontin, ST2, IL-10, and Galectin-3
  - Exploratory biomarkers (if consent/assent provided)
  - Immunoassay: DSA
- A urine sample will be collected for urinalysis
- PUL Scale
- 6MWT (if capable)
- Pediatric QL Inventory
- PODCI
- Spirometry

## 7.7 Month 6 Visit (Day 180 ± 14 days)

Subjects will return to the clinical site and complete the following procedures:

- Adverse event assessment
- Review of concomitant medications
- Measurement of vital signs (temperature, HR, BP, and RR), weight and height
- 12-Lead ECG
- Cardiac Physical Examination
- Cardiac MRI
  - Seven day continuous cardiac rhythm monitoring using sponsor-supplied device
- Venous blood will be collected for the following:
  - Clinical laboratory tests: serum chemistry, hematology, and cystatin C
  - Biomarkers: Osteopontin, ST2, IL-10, and Galectin-3
  - Exploratory biomarkers (if consent/assent provided)
  - Immunoassay: DSA
  - Cardiac enzymes: Troponin and CK-MB
- A urine sample will be collected for urinalysis
- PUL Scale
- 6MWT (if capable)
- Pediatric QL Inventory
- PODCI
- Spirometry

## 7.8 Month 12 Visit (Day 360 ± 30 days)

Subjects will return to the clinical site and complete the following procedures:

- Adverse event assessment
- Review of concomitant medications
- Measurement of vital signs (temperature, HR, BP, and RR), weight and height
- 12-Lead ECG
- Cardiac and limited physical examinations
- Cardiac MRI
- 72 hour continuous cardiac rhythm monitoring using sponsor-supplied device
- Venous blood will be collected for the following:
  - Clinical laboratory tests: serum chemistry, hematology, and cystatin C
  - Biomarkers: Osteopontin, ST2, IL-10, and Galectin-3
  - Exploratory biomarkers (if consent/assent provided)
  - Immunoassay: DSA
  - Cardiac enzymes: Troponin and CK-MB
- A urine sample will be collected for urinalysis
- PUL Scale
- 6MWT (if capable)
- Pediatric QL Inventory
- PODCI
- Spirometry

## 7.9 Annual Follow-up Phone Call

Following a subject's last site visit, annual follow-up phone calls will be conducted for an additional four years for subjects that provide consent and/or assent. Subjects will be contacted by phone annually ( $\pm$  2 weeks) on the anniversary of their Day 0 through year 5 to assess for acute or planned procedure and/or admission for cardiac cause as well as survival. These annual follow-up phone calls will continue in concert with a subject's normal, annual clinical follow-up which may include annual cardiac MRI where clinically indicated.

## 7.10 Removal of Patients from the Trial or Study Drug

The Investigator may withdraw a subject from participation in the study for any of the following reasons:

- A significant protocol violation occurs,
- An intolerable adverse event occurs, that affects continuation of subject's participation in the study,
- The Sponsor or Investigator terminates the study, or
- The subject requests to be discontinued from the study.

If a subject wishes to discontinue study participation solely for the purpose of enrolling in another clinical trial or expanded access protocol, the investigator should make every attempt to continue to collect follow-up medical information for the subject per this trial's schedule. This specific category of protocol violation (receipt of prohibited medications) will be managed as defined in the SAP.

## **7.11 Early Termination Procedures**

Every reasonable effort will be made to retain subjects in the study. In the event that a subject must be withdrawn from the study early, study personnel should attempt to obtain testing and data required for the 12 Month Visit (see Section 7.8) as well as the reason for withdrawal, if known. A Cardiac MRI will be conducted provided the subject's most recent study-related Cardiac MRI was conducted at least three months (i.e., 12 weeks) prior to the Early Termination Visit.

If the subject permits, he or she should be contacted by study personnel at the time of their usual study visits (and annually through 5 years post-infusion), as described in the protocol.

## **7.12 Lost to Follow-Up**

A subject can be considered "lost to follow-up" if he misses a visit and study personnel are unable to contact him, or parent(s)/guardian(s) as applicable, in a timely manner with a minimum of three documented phone calls. If contact with the subject, or parent(s)/guardian(s) as applicable, is not accomplished, study personnel should follow-up with certified mail in the following manner:

1. Mail a certified letter with return receipt requesting contact and expressing concern for the subject's well-being.
2. If the subject, or parent(s)/guardian(s) as applicable, does not respond within seven days, mail another certified letter with return receipt stating that the subject's participation in the study has been terminated.
3. If a signed mailing receipt for the second letter is returned, record the termination date as the date the subject, or parent(s)/guardian(s) as applicable, signed it. Otherwise, record the termination date as the date the second letter was mailed.

If, despite the efforts noted above, it is necessary to classify a subject as lost to follow-up, that subject's End of Study (EOS) is the date/time of last contact or known event (inclusive of study visits, telephone contacts, or other verification of subject survival or mortality).

## 7.13 Adverse Events Assessments

### 7.13.1 Performing Adverse Events Assessments

An Adverse Event (AE) is any untoward medical occurrence in a subject or clinical investigation subject temporally associated with the use of a medicinal product, whether or not considered related to the medicinal product. The occurrence does not necessarily have to have a causal relationship with this treatment. An AE can therefore be any unfavorable and unintended sign (including an abnormal laboratory finding, for example), symptom, or disease (new or exacerbated) temporally associated with the use of a medicinal product, whether or not considered related to the medicinal product.

Examples of an AE include:

- Exacerbation of a chronic or intermittent pre-existing condition including either an increase in frequency or intensity of the condition.
- Significant or unexpected worsening or exacerbation of the condition/indication under study.
- A new condition detected or diagnosed after study therapy administration even though it may have been present prior to the start of the study.
- Pre- or post-treatment events that occur as a result of protocol-mandated procedures (e.g., invasive protocol-defined procedures, modification of a subject's previous treatment regimen).

An AE does not include:

- Medical or surgical procedures (e.g., colonoscopy, biopsy). The medical condition that leads to the procedure is an AE.
- Social or convenience hospital admissions where an untoward medical occurrence did not occur.
- Day to day fluctuations of pre-existing disease or conditions present or detected at the start of the study that do not worsen.
- The disease/disorder being studied or expected progression, signs, or symptoms of the disease/disorder being studied unless more severe than expected for the subject's condition.

The Investigator will review all documentation (e.g., hospital progress notes, laboratory, or diagnostic reports) relative to the event being reported. The Investigator will then record all relevant information regarding an AE/SAE into the data system. It is not acceptable for the Investigator to send photocopies of the subjects' medical records in lieu of completion of the appropriate AE/SAE pages. However, there may be instances when the Medical Monitor (an independent physician who is not participating in the clinical study), requests copies of medical records for certain cases. In this instance, all subject identifiers will be blinded on the copies of the medical records prior to submission to the Medical Monitor.

The Investigator will attempt to establish a diagnosis of the event based on signs, symptoms, and/or other clinical information. In such cases, the diagnosis should be documented as the AE/SAE and not the individual signs and symptoms.

